6.1.2.2. Visit 3 (Day 120; ~4 Months)

Patients will return to the Research Site for Visit 3 on Day 120 ± 10 days.

The following procedures will be performed:

- Perform physical examination
- Obtain weight
- Obtain vital signs (systolic and diastolic blood pressure, heart rate, respiratory rate, and body temperature)
- Obtain fasting blood samples for:
 - Chemistry and hematology testing
 - Lipid profile

- Review study drug compliance by unused capsule count; discuss with and counsel patients about compliance if needed
- Administer study drug - Note: Study drug should be taken orally with food following the collection of all fasting blood samples
- Assess and record efficacy events
- Assess for and record adverse events
- Record concomitant medication(s)
- Instruct patient:
 - To bring all study supplies with them to the next visit
 - Not to take study drug on the morning of their next visit
 - To fast for ≥ 10 hours prior to the next visit

6.1.2.3. Visits 4, 5, 6, 7, 8 and 9

At Visit 4: Day 360 ± 10 ; Visit 5: Day 720 ± 10 ; Visit 6: Day 1080 ± 10 ; Visit 7: Day 1440 ± 10 , Visit 8: Day 1800 ± 10 , Visit 9: Day 2160 ± 10) the following procedures will be performed:

- Perform physical examination
- Obtain weight
- Obtain vital signs (systolic and diastolic blood pressure, heart rate, respiratory rate, and body temperature)
- Measure waist circumference (collected at Visit 5 only)
- Obtain a 12-lead ECG
- Obtain fasting blood samples for:
 - Chemistry and hematology testing
 - Lipid profile
 - Biomarker assays (collected at Visit 5 only)
 - Archiving (in countries and at sites approved by IRB/IEC and dependent on country regulations)
- Review study drug compliance by unused capsule count; discuss with and counsel patients about compliance if needed
- Administer study drug - Note: Study drug should be taken orally with food following the collection of all fasting blood samples
- Assess and record efficacy events
- Assess for and record adverse events
- Record concomitant medication(s)
- Instruct patient:

- To bring all study supplies with them to the next visit
- Not to take study drug on the morning of their next visit
- To fast for ≥ 10 hours prior to the next visit

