6.3.1.4. Biomarkers Assays

The biomarker assays include: hs-CRP, Apo B and hsTnT.

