APPENDIX A: SCHEDULE OF PROCEDURES

Study Day	Screening		Follow-Up (FU) ¹³								
	Up to 42 days before Day 0	If a Visit 1.1 takes place, Visit 1 may occur up to 60 days before Day 0 ²	0	120 ± 10	360 ± 10	720 ± 10	1080 ± 10	1440 ± 10	1800 ± 10	2160 ± 10	Last Visit (LV) ¹⁵
Months of FU			0	4	12	24	36	48	60	72	(varies)
Years of FU			0	0.33	1	2	3	4	5	6	(varies)
Visit #	1	1.1	2	3	4	5	6	7	8	9 ¹⁴	LV
Study Procedures:											
Informed Consent	X										
Medical, Surgical & Family History	X										
Demographics	X										
Evaluate inclusion / exclusion criteria	X ¹	X ³	X								
Physical Examination			X	X	X	X	X	X	X	X	X
Weight, Height ⁴	X		X	X	X	X	X	X	X	X	X
Vital Signs ⁵	X	X	X	X	X	X	X	X	X	X	X
Waist Circumference			X			X					X
12-Lead ECG	X		X		X	X	X	X	X	X	X
Urine pregnancy test ⁶	X		X								
Concomitant Meds	X	X	X	X	X	X	X	X	X	X	X
Randomization			X								
Dosing at the Research Site ⁷			X	X	X	X	X	X	X	X	
Efficacy events				X	X	X	X	X	X	X	X
AE Evaluations			X	X	X	X	X	X	X	X	X
Compliance Check ⁸				X	X	X	X	X	X	X	X
Chemistry ⁹ and hematology	X	X ³	X	X	X	X	X	X	X	X	X
Fasting lipid profile ¹⁰	X	X ³	X	X	X	X	X	X	X	X	X
Genetic testing ¹¹			X								
Biomarkers: hs-CRP, apo B, hsTNT			X			X					X

Study Day	Screening		Follow-Up (FU) ¹³								
	Up to 42 days before Day 0	If a Visit 1.1 takes place, Visit 1 may occur up to 60 days before Day 0 ²	0	120 ± 10	360 ± 10	720 ± 10	1080 ± 10	1440 ± 10	1800 ± 10	2160 ± 10	Last Visit (LV) ¹⁵
Months of FU			0	4	12	24	36	48	60	72	(varies)
Years of FU			0	0.33	1	2	3	4	5	6	(varies)
Visit #	1	1.1	2	3	4	5	6	7	8	9 ¹⁴	LV
Fasting blood sample for archiving ¹²			X		X	X	X	X	X	X	X

- Includes procedures and (fasting) blood samples (for example, hs-CRP, calculated creatinine clearance) as needed to determine the CV risk category (see inclusion criteria).
- Screening visit to re-evaluate inclusion/exclusion criteria for patients who are not eligible for participation based on data from Visit 1.
- Inclusion/exclusion criteria will be re-evaluated for selected study procedures that are performed on Visit 1.1 because patients failed to meet them at Visit 1.
- Height at first screening visit only.
- Vital signs, including systolic and diastolic blood pressure (mmHg), heart rate, respiratory rate and body temperature. Participants must be seated for at least 5 minutes before assessments of vital signs.
- For women of childbearing potential.

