- Composite of CV death, nonfatal MI (including silent MI), non-elective coronary revascularizations (defined as emergent or urgent classifications), or unstable angina determined to be caused by myocardial ischemia by invasive/non-invasive testing and requiring emergent hospitalization;
- Composite of CV death, nonfatal MI (including silent MI), non-elective coronary revascularizations (defined as emergent or urgent classifications), unstable angina determined to be caused by myocardial ischemia by invasive/non-invasive testing and requiring emergent hospitalization, nonfatal stroke, or PVD requiring intervention, such as angioplasty, bypass surgery, or aneurism repair;
- Composite of CV death, nonfatal MI (including silent MI), non-elective coronary revascularizations (defined as emergent or urgent classifications), unstable angina determined to be caused by myocardial ischemia by invasive/non-invasive testing and requiring emergent hospitalization, PVD requiring intervention, or cardiac arrhythmia requiring hospitalization of ≥ 24 hours;
- New CHF;
- New CHF as the primary cause of hospitalization;
- Transient ischemic attack (TIA);
- Amputation for PVD;
- Carotid revascularization;
- All coronary revascularizations defined as the composite of emergent, urgent, elective, or salvage;
- Emergent coronary revascularizations;
- Urgent coronary revascularizations;
- Elective coronary revascularizations;
- Salvage coronary revascularizations;
- Cardiac arrhythmias requiring hospitalization of ≥ 24 hours;

- Cardiac arrest;
- Ischemic stroke;
- Hemorrhagic stroke;
- Fatal or nonfatal stroke in the subset of patients with a history of stroke prior to baseline;
- New onset diabetes, defined as Type 2 diabetes newly diagnosed during the treatment/follow-up period;
- New onset hypertension, defined as blood pressure ≥ 140 mmHg systolic OR ≥ 90 mmHg diastolic newly diagnosed during the treatment/follow-up period;
- Fasting TG, TC, LDL-C, HDL-C, non-HDL-C, VLDL-C, apo B, hs-CRP (hsCRP and $\log[\text{hsCRP}]$), hsTnT, and RLP-C (to be estimated from standard lipid panel, $\text{RLP-C} = \text{TC} - \text{HDL-C} - \text{LDL-C}$ [Varbo 2014]) (based on ITT estimands):
 - Assessment of the relationship between baseline biomarker values and treatment effects within the primary and key secondary composite endpoints,

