 - Assessment of the relationship between post-baseline biomarker values and treatment effects within the primary and key secondary composite endpoints by including post-baseline biomarker values (for example, at 4 months, or at 1 year) as a covariate.

Continuous tertiary endpoints include:

- Change from baseline and percent change from baseline in fasting TG, TC, LDL-C, HDL-C, non-HDL-C, VLDL-C, apo B, hs-CRP (hsCRP and $\log[\text{hsCRP}]$), hsTnT, and RLP-C (to be estimated from standard lipid panel, $\text{RLP-C} = \text{TC} - \text{HDL-C} - \text{LDL-C}$ [Varbo 2014]) (based on ITT estimands);
- Change in body weight;
- Change in waist circumference.

The fasting lipid panel is tested at Screening (Visit 1 or Visit 1.1), Randomization visit (Visit 2; Day 0), Visit 3 (Day 120; ~4 Months) and all other follow-up visits including the last visit. For change from baseline to 1-year Preparative Ultracentrifugation measurements for LDL-C will be analysed, unless this value is missing. As described in Section 4.3.3, if the LDL-C Preparative Ultracentrifugation values is missing, then another LDL-C value will be used, with prioritization of values obtained from LDL-C Direct measurements, followed by LDL-C derived by the Friedewald calculation (only for subjects with TG < 400 mg/dL), and finally LDL-C derived using the calculation published by Hopkins University investigators (Martin 2013). In addition, change from baseline to day 120 in LDL-C utilizing Friedewald's and Hopkins methods will be analysed, using the arithmetic mean of LDL-C obtained at Visit 2 (Day 0) and the preceding Visit 1 (or Visit 1.1). If one of these values is missing, the single available LDL-C value will be used. LDL-C according to Hopkins will be calculated at each visit.

The randomization visit will be considered Baseline. If a baseline value is not available from the randomization visit, then the latest screening value will be used.

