For measurements of lipids, lipoproteins, and inflammatory markers, the change from baseline and the percent change will be summarized at each visit. Since these parameters are typically not normally distributed, the Wilcoxon rank-sum test will be used for treatment comparisons of the percent change from baseline, and medians and quartiles will be provided for each treatment group. The medians of the differences between the treatment groups and 95% CIs will be estimated with the Hodges-Lehman method. In addition, shift-tables may be generated as appropriate.

As an additional exploratory analysis, the relationship between post-baseline biomarker values and treatment effects with the primary and key secondary composite endpoints will be assessed by adding biomarker values (for example, at 4 month, or at 1 year, etc.) as time-dependent covariates in the Cox proportional hazards model. Diagnostic plots for the proportional hazards assumption will be evaluated.

Weight is measured at the screening visit and at all follow-up visits, including the last visit of the study. Waist circumference will be measured at the randomization visit (Visit 2; Day 0), Visit 5 (Day 720) and the last visit of the study. Descriptive statistics will be presented by visit and treatment group for baseline, post-treatment change from baseline, and the percent change from baseline. Analysis methods for repeated measurements will be used to compare percent change from baseline between treatments.

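### hs-CRP, apo B and hsTnT have no scheduled sample between Day 0 and Day 720, so the 4-month and 1-year covariate examples cannot apply to them, and a Day 720 value needs a rule for earlier events

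*Combined protocol and SAP*

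**What the plan says.** SAP 4.7.4 (Analysis of Tertiary Endpoints) opens the marker item with "Fasting TG, TC, LDL-C, HDL-C, non-HDL-C, VLDL-C, apo B, hs-CRP" and continues with hsTnT and RLP-C, ten markers in all. Their post-baseline values are to be related to the treatment effect on the primary and key secondary composites "by including post-baseline biomarker values (for example, at 4 months, or at 1 year) as a covariate". Later in the same section a second form of the analysis enters the values "as time-dependent covariates in the Cox proportional hazards model", with the same two times as examples. The tertiary time-to-event analyses use the ITT population, run from randomization and follow the primary endpoint's censoring rules.

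The protocol splits the ten markers into two sampling schedules.

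- **Lipid panel** (protocol 6.3.1.2: TG, TC, LDL-C, HDL-C, non-HDL-C, VLDL-C): drawn at Visit 3 (Day 120) and every later visit. RLP-C is calculated from it.
- **Biomarker panel** (protocol 6.3.1.4): "The biomarker assays include: hs-CRP, Apo B and hsTnT". It is drawn at Visit 2. Visit 3 lists no such draw. For Visits 4 to 9, protocol 6.1.2.3 has "Biomarker assays (collected at Visit 5 only". The Last Visit (6.1.2.5) adds one more. In protocol Appendix A, the row "Biomarkers: hs-CRP, apo B, hsTNT" is marked at Day 0, Day 720 and the Last Visit only.

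SAP Addendum section 6 adds an on-treatment hsCRP analysis that groups patients by their values at baseline and at 2 years, analysed as for the ITT population. Section 3 of the Pre-Specified List of Additional Analyses also looks at hsCRP at 2 years and at end of study.

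**The concern.** For three of the ten markers the only times that SAP 4.7.4 names have no scheduled measurement. The earliest scheduled post-baseline value is at Day 720, and the SAP gives no rule for events that come before it.

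This matters differently in the two forms of the analysis. If a Day 720 value enters a model that starts at randomization, a patient with a nonfatal event in year 1 contributes a marker measured after the outcome it is meant to help explain. Patients who die or leave before Visit 5 have no value, and SAP 4.3.2 makes no imputation the default. The problem is sharpest for hsTnT, because troponin is itself one of the criteria for MI in protocol Appendix B: a later value may reflect the event. In the time-dependent form no future value is used, but until Day 720 the model knows only the baseline value, or nothing.

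What is at stake is the exploratory question of whether change in inflammation, apo B or troponin accounts for any treatment effect. The protocol's rationale (section 1.4) itself raises mechanisms other than lipid lowering, and hs-CRP and hsTnT are the non-lipid markers in this list.

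**Working it through.** **Schedule against the named times**

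| Marker | Day 120 | Day 360 | Day 720 |
|---|---|---|---|
| TG, TC, LDL-C, HDL-C, non-HDL-C, VLDL-C, RLP-C (7) | yes | yes | yes |
| hs-CRP, apo B, hsTnT (3) | no | no | yes |

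The other scheduled sample for the three is at the Last Visit. Protocol 6.1.2.5 targets that visit within 30 days after the study end date and counts efficacy events only up to that date, so the Last Visit sample will normally follow every counted event. Day 720 is in practice the only scheduled post-baseline value that can precede an event.

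**Inputs** (SAP 4.1; allocation from SAP 3.2): N = 7990 randomized 1:1, so 3995 per arm; one-year control event rate 5.2%; HR 0.85; constant hazard; no dropout; accrual 20/40/20/19% in years 1 to 4 and 1% in the last 0.2 years; study length 6.5 years.

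**Hazards.** Control: −ln(1 − 0.052) = 0.0534 per year (printed as 0.053). Active: 0.85 × 0.0534 = 0.0454.

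**Step 1: reproduce the plan's 1612 events.** A patient entering at time e has event probability 1 − exp(−λ(6.5 − e)). The averages over the five entry bands are:

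- control: 0.2741, 0.2342, 0.1922, 0.1479, 0.1203;
- active: 0.2383, 0.2030, 0.1660, 0.1272, 0.1032.

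Weighted by 0.20, 0.40, 0.20, 0.19 and 0.01:

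- control: 0.2162 × 3995 ≈ 864 events;
- active: 0.1873 × 3995 ≈ 748 events;
- total: 1612, which is the plan's figure. The rounded hazard 0.053 gives 1601.

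**Step 2: events by each patient's own Day 720.** The last patient enters at 4.2 years, so everyone has at least 6.5 − 4.2 = 2.3 years of planned follow-up and the cut applies to all. With t = 720/365.25 = 1.971 years:

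- control: 1 − exp(−0.0534 × 1.971) = 0.0999, × 3995 = 399;
- active: 1 − exp(−0.0454 × 1.971) = 0.0856, × 3995 = 342;
- total: 741, and 741/1612 = 46.0%.

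Events left after Day 720: 1612 − 741 = 871.

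**Step 3: the same sum at the two named times.** Day 120: 129 events (8.0%). Day 360: 380 events (23.5%). So a lipid value used as a fixed covariate has the same ordering problem on a smaller scale.

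**Sensitivity of the 46%**

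| Change | Share by Day 720 |
|---|---|
| Hazard 0.053 instead of 0.0534 | 45.9% |
| HR 1.0 | 46.2% |
| Assumed dropout of 1% to 3% per year | 46.6% to 47.8% |
| Study length 7.0 years | 42% |
| Study length 6.0 years | 51% |

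Dropout rates are not in the documents; that row is an assumption.

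**The case against.** The strongest reply is that the two times are only examples, and the time-dependent paragraph adds an open-ended etc. to them. They work for seven of the ten markers, and nothing commits hs-CRP, apo B or hsTnT to them. That stands: this is shared wording that fits most of the list. But the SAP names no other time for the three, whereas in the same section it gives the actual visits for waist circumference (randomization, then "Visit 5 (Day 720) and the last visit of the study").

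Second, the later documents already use 2 years for hsCRP. True, and that fits the schedule. It leaves apo B and hsTnT untouched, and the Addendum's grouping keeps the randomization clock, so earlier events are still counted against a later value. The 1-year and 2-year landmarks in Addendum sections 4 and 5 do not help: they keep events before the landmark and censor everyone else there, the reverse of what is needed.

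Third, a reader might infer that no patient can have an earlier value. The documents do not support that. Archived serum is drawn at Visit 4 and could give 1-year values, though only at approved sites and at the sponsor's discretion (protocol 6.3.1.5), and none is drawn at Visit 3. Patients off study drug have an interim visit with Visit 5 procedures (protocol 11.1), possibly before Day 720, but they are a selected subset.

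Fourth, a reader might infer that the time-dependent Cox model also conditions on the future. It does not, and no passage says that baseline is carried forward. What is missing is a rule for the time before Visit 5.

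**Conclusion.** The point holds for three markers in exploratory analyses. For hs-CRP, apo B and hsTnT the named times have no scheduled sample, and about 46% of primary events (741 of 1612; 42% to 51% for a study length of 7.0 to 6.0 years) are expected before the first scheduled post-baseline value. A fixed covariate from randomization, or the Addendum's 2-year hsCRP grouping, would use values that follow many of the events and are missing for patients who die or leave earlier. The time-dependent model is sound in principle. For events in the first two years it is uninformative about change in these markers, or attenuated if baseline is carried forward.

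The 46% is a design expectation under constant hazard, HR 0.85, the planned accrual and no dropout; it is not an observed count. Nor does it measure bias or missing data. Most components are nonfatal and follow-up continues after an event, so many of those patients would still have a Visit 5 sample, only too late. The number who die or leave before Visit 5 cannot be derived from the documents.

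A reader might also infer that the trial's main results are at risk. They are not: SAP 4.3.6 classes the tertiary analyses as exploratory, and no primary or secondary conclusion depends on them.

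**What to change.** Amend the wording of SAP 4.7.4 and Addendum section 6 before unblinding.

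- **hs-CRP, apo B and hsTnT, including the 2-year hsCRP grouping:** start the clock at the Visit 5 sample. Include patients who are in follow-up, free of the endpoint analysed and have a Visit 5 value. Count only later events. Equivalently, let patients enter the risk set of the time-dependent model only from Visit 5.
- **Interpretation:** state that the result applies to events after year 2, in a selected group that is no longer the full randomized comparison.
- **Lipid-panel markers and RLP-C:** keep the 4-month and 1-year values. Where one is used as a fixed covariate, count only events after that measurement.

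The cost is SAP wording, with no new visits or assays. For the three markers the primary-endpoint analysis then rests on about 870 expected events at most, fewer if Visit 5 samples are missing. For a fixed lipid covariate, the rule sets aside about 8% of expected primary events at 4 months or 24% at 1 year.

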3.6. Number of Patients

This is an event-driven trial: It is expected that a minimum of approximately 1612 primary endpoint events will be required during the study. A total of approximately 7990 patients will be entered into the study to either receive AMR101 or placebo (approximately 3995 patients per treatment group) in order to observe an estimated 1612 events that make up the primary composite endpoint for efficacy. Additional patients may be enrolled beyond the projected 7990 if the number of events contributing to the primary endpoint appears less than, and inconsistent with, projections (see [Section 12.3](#)).

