3.2 Study Design

This is a Phase 3b, multi-center, multi-national, prospective, randomized, double-blind, placebo-controlled, parallel-group study.

This is an event driven trial comparing the effect of AMR101 vs. control, in terms of the composite endpoint listed above as the primary efficacy endpoint. The study has been planned to accrue a total of 1612 efficacy endpoint events with two planned interim analyses when approximately 967 (60%) and 1290 (80%) of the events have occurred and been adjudicated. The study includes patients with established CVD (CV Risk Category 1) and patients ≥ 50 years old with diabetes and at least one additional risk factor for CVD but with CVD not established (CV Risk Category 2).

Sample size calculation was based on assumptions of constant hazard, asymmetric recruitment rate over time and without factoring for dropouts. A risk reduction corresponding to a hazard ratio of 0.85 (AMR101 vs. control) is assumed. 1612 events would be required to detect this hazard ratio with approximately 90% power with one-sided alpha-level at 2.5% and with two interim analyses.

The recruitment period is assumed to be approximately 4.2 years with 20% recruitment in the first year, 40% in the second year, 20% in the third year, 19% in the fourth year and the remaining 1% in the last 0.2 years. The expected maximum study duration is estimated at 6.5 years unless the trial is terminated early for efficacy or safety issues. A one-year event rate of 5.2% (hazard = 0.053) in the control arm is also assumed. Under these assumptions the number of patients to be enrolled is $N = 7990$.

Randomized treatment assignment to either 4 g/day AMR101 or placebo in a 1:1 ratio will be provided using the internet via an interactive web response system (IWRS). Randomization will be stratified by CV Risk Category 1 or 2 (defined in the inclusion criteria of the study protocol), use of ezetimibe, and by geographical region (Westernized, Eastern European, and Asia Pacific countries).

Approximately 70% of randomized patients will be in CV Risk Category 1, and approximately 30% of randomized patients will be in CV Risk Category 2. Enrollment of patients within a CV risk category will be stopped when the planned number of patients in that risk category is reached or, if the enrollment target is extended beyond 7990 patients (as

described in Section 4.1), then only CV Risk Category 1 will be included in further enrollment.

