4.3 Statistical Considerations

4.3.1 General Statistical Considerations

All statistical analyses and data summaries are to be generated according to this SAP. Any deviations from this SAP will be documented in the CSR.

All null hypotheses will be defined as no treatment difference. All statistical tests for the efficacy outcomes will be performed at the two-sided 5% significance level, unless otherwise noted. The iSAP will utilize one-sided testing for efficacy at the 0.025 level for interim analyses, the operating characteristics of which are identical to those of a corresponding group sequential design with a two-sided alpha level of 0.05.

Summary statistics will be presented by treatment group and by visit where appropriate. Data will be presented “as-observed”, unless otherwise specified. Continuous data will be summarized with descriptive statistics: count (n), number of missing values (n-missing), mean, standard deviation (SD), median, minimum, and maximum. Categorical data will be described using frequencies and percentages, including a category for missing values where appropriate. Percentages are based on the number of patients in the analysis set. All meaningful patient data collected in the database will be listed. Listings will be sorted by patient within center/site.

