Since the results from the analysis of the tertiary endpoints are intended to be supportive rather than pivotal evidence of drug efficacy and safety, all tertiary efficacy endpoint analysis will be considered exploratory and statistical testing will be carried out at the nominal 5% level without adjustment.

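### SAP 4.7.4 tests percent change from baseline in log[hsCRP], which reverses sign below 1 mg/L, is undefined at 1 mg/L and depends on the unit, so its estimate cannot be interpreted

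*Combined protocol and SAP*

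**What the plan says.** SAP 4.7.4 names, among the continuous tertiary endpoints, "Change from baseline and percent change from baseline in fasting TG, TC, LDL-C, HDL-C, non-HDL-C, VLDL-C, apo B, hs-CRP (hsCRP and $\log[\text{hsCRP". The bracket covers hsCRP and its logarithm, so both change and percent change are listed for both forms.

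For lipids, lipoproteins and inflammatory markers the same section states that "the change from baseline and the percent change will be summarized at each visit". For the comparison between arms, "the Wilcoxon rank-sum test will be used for treatment comparisons of the percent change from baseline", with medians and quartiles by group. The reported estimate follows: "The medians of the differences between the treatment groups and 95% CIs will be estimated with the Hodges-Lehman method". No exception is made for log[hsCRP], no test is named for absolute change, and there is no rule for a zero denominator.

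SAP 4.3.6 classes all tertiary analyses as exploratory, and "statistical testing will be carried out at the nominal 5% level without adjustment". Protocol 12.2.4.4 has the same percent-change test but does not mention log[hsCRP]. Protocol 9.2.3 lists log[hsCRP] as a marker without attaching percent change to it. The explicit pairing is in the SAP.

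No unit is given for the logarithm. The hsCRP cut points in protocol 12.2.4.5 and SAP 4.7.5 are in mg/L; Section 6 of the SAP Addendum writes its hsCRP cut point of 2 in mg/dL.

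**The concern.** Percent change needs a scale with a true zero. On a log scale, zero is only the point where hsCRP equals one unit. Dividing by the baseline log reverses the sign for every patient below that point and inflates the value for patients close to it. Improvements and worsenings are then ranked together.

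The log form is normally used to deal with the skew of hsCRP, and here the one comparison specified for it is on an invalid scale. At stake is a report with two hsCRP rows, raw and log, that could disagree in size, significance or direction for purely arithmetic reasons.

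**Working it through.** The plan states no effect size, SD or power for hsCRP, so there is no figure of its own to reproduce.

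**Step 1: the arithmetic, with no assumptions.** Let x be the log of baseline hsCRP and d the change in log. The tested quantity is 100·d/x. For a true 20% fall, d = ln 0.8 = -0.223 in every patient.

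| Baseline, mg/L | x | 100·d/x |
|---|---|---|
| 0.5 | -0.693 | +32% |
| 0.8 | -0.223 | +100% |
| 0.95 | -0.051 | +435% |
| 1.0 | 0 | undefined |
| 1.05 | +0.049 | -457% |
| 1.1 | +0.095 | -234% |
| 3.0 | +1.099 | -20% |
| 5.0 | +1.609 | -14% |

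The log base cancels; the unit does not. A baseline of 3.0 mg/L is 0.30 mg/dL, and ln 0.8 / ln 0.3 = -0.223 / -1.204, or +18.5%, where mg/L gave -20%.

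**Step 2: how many patients are affected (assumed distribution).** If hsCRP is lognormal with median m and log-SD s, the share with a negative baseline log is Φ(-ln m / s). For m = 1.5, s = 1.1 this is Φ(-0.369) = 36%; for m = 3.0, s = 0.9 it is Φ(-1.221) = 11%.

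**Step 3: power at the planned size.** Inputs from the documents: "approximately 3995 patients per treatment group" (protocol 3.6), 1:1 allocation (SAP 3.2), two-sided 5% (SAP 4.3.1, 4.3.6). Assumed: log-SD 1.0; d normal with SD 0.8 around the treatment effect, less 0.3·(x - ln m) for regression to the mean. Simulated Wilcoxon power, 3995 per arm:

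| Median, mg/L | True reduction | 100·d/x | d |
|---|---|---|---|
| 1.5 | 10% | about 27% | about 100% |
| 2.2 | 10% | 71% | 100% |
| 3.0 | 10% | about 93% | about 100% |
| 2.2 | 5% | 22% | 75% |
| 2.2 | 20% | 100% | 100% |

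**Step 4: a wider range.** Bivariate lognormal hsCRP, log-SD 0.9 or 1.1, baseline to follow-up correlation 0.5 or 0.7, 3995 per arm, Monte Carlo error up to about 4 points:

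| Median, mg/L | Share below 1 | Power, 10% reduction | Power, 20% reduction | Relative efficiency |
|---|---|---|---|---|
| 1.0 | 50% | 1-5% (correct direction) | 1-5% (correct direction) | about 0 |
| 1.5 | 33-36% | 23-50% | 55-97% | 0.05-0.10 |
| 2.0 | 22-26% | 46-83% | 97-100% | 0.12-0.28 |
| 3.0 | 11-16% | 79-99% | 100% | 0.32-0.58 |

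Testing d instead gives 97-100% for a 10% reduction and 100% for 20%. With 3000 per arm to allow for missing samples (median 2.0, log-SD 1.1, correlation 0.5), a 10% reduction has 31% against 98%, and a 20% reduction 89% against 100%. If the log were taken in mg/dL, a true 20% reduction tested as a significant increase in every replicate, at medians of 1.5, 2 and 3 mg/L.

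**Step 5: what the plan already has.** Percent change in untransformed hsCRP is 100·(exp(d) - 1), which rises strictly with d. The ranks are the same, so the planned Wilcoxon test on it is identical to a Wilcoxon test on the difference in logs. In simulation the two statistics never differed.

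**The case against.** The strongest reply is that nothing important is lost. The valid test is already planned through untransformed hsCRP (Step 5), with an interpretable Hodges-Lehmann interval. Change in log[hsCRP] is listed and summarized. The endpoint is tertiary and exploratory, and no primary, secondary, interim or safety conclusion rests on it. The Wilcoxon test uses ranks, so extreme values near 1 mg/L have bounded influence. All of this stands and limits the impact. It does not rescue the log[hsCRP] row, whose median and estimate remain meaningless if the SAP is followed as written.

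A reader might infer that the log[hsCRP] test loses most of its power. The documents do not support that as a general statement. They give no hsCRP distribution, and at about 3995 per arm power for a 20% reduction stays at 97-100% when the assumed median is 2 mg/L or more. Large losses need a small effect or a median near 1 to 1.5 mg/L.

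A reader might also infer that the trial cannot assess the drug's effect on hsCRP. Step 5 rules that out.

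On units, nearly all hsCRP cut points are in mg/L, and the mg/dL in the Addendum belongs to a subgroup definition. A mg/dL logarithm is therefore a risk left open by silence, not something the plan calls for.

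**Conclusion.** The SAP is wrong as written on one exploratory output. The sign reversal, the undefined value at 1 mg/L and the dependence on the unit are exact and need no assumptions; they make the median and Hodges-Lehmann estimate for log[hsCRP] uninterpretable.

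The size of the efficiency loss does rest on assumptions. For a 10% reduction, power falls from about 100% to somewhere between about 27% and 93% over assumed medians of 1.5 to 3.0 mg/L (log-SD 1.0, within-patient SD 0.8, 3995 per arm). For a 20% reduction little is lost at a median of about 2 mg/L or more. The hsCRP comparison itself survives through the untransformed marker. This is a small defect that should be corrected, with no bearing on the trial's main conclusions.

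**What to change.** In SAP 4.7.4, limit percent change to untransformed hsCRP. For log[hsCRP], specify change from baseline (the difference in logs) as the quantity compared between arms, back-transformed to a ratio of geometric means with a 95% CI, and state that hsCRP is in mg/L before the log is taken.

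In protocol 12.2.4.4, add that the percent-change test does not apply to log[hsCRP]; there is no log[hsCRP] wording there to remove.

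The cost is a line of text in each document and a minor programming change. No new data are needed.
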